- ^m Pharmacokinetic and ADA blood sampling will be taken prior to administration of study drug (pre-dose) on dosing days.
- ⁿ Administration of study drug should be done last after all study procedures unless indicated otherwise. Subjects will be monitored at the study site for at least one hour after study drug administrations at the following visits: for subjects enrolled to QW arms, on Day 1 and Weeks 1, 16, and 17; for subjects enrolled to Q2W arms, on Day 1 and Weeks 2, 16, and 18. After Week 4, qualified subjects may perform home dosing of study drug at weeks without study visits (see footnote a) and do not need to return to the clinical site on those weeks. Subjects may begin self-administration of study drug from Week 5 (QW dosing) or Week 6 (Q2W dosing). Subjects will be trained on study drug handling and self-administration of study drug at the study visits prior to beginning self-administration. A subject's caregiver or designee can also be trained on home dosing based on the subject's preference. Study-site staff will administer study drug at the first 2 visits. Thereafter, if home dosing is a consideration, the subject or subject's caregiver or designee must administer and demonstrate competency

for at least 2 visits prior to being allowed to dose at home. Otherwise, the subject will need to return to the site for all injections. The last dose of study drug for subjects dosed QW is Week 31 and for subjects dosed Q2W is Week 30.

[°] A dosing diary will be completed for every home dosing administration.

^p Subjects who end the study early will complete an early termination visit and complete the procedures described at the Week 32 visit within 2 weeks of the last dose of study drug.

2. Introduction

Izokibep is a potent and selective inhibitor of interleukin 17A (IL-17A) that is being developed for treatment of hidradenitis suppurativa (HS).

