9.3.5. Safety Analyses

Safety data will include summaries of exposure, AEs, SAEs, and laboratory data. Safety will be reported separately for Parts A and B of the study. In Part B, subjects who received placebo QW and placebo Q2W will be combined for summaries during the placebo-controlled portion of the study. No inferential statistics (p-values) will be reported for safety data.

Exposure will include the number of doses administered (including complete and incomplete doses) and reasons for missed or incomplete doses. Exposure will be reported through the planned collection of the primary endpoint and for the entire study. For subjects assigned to receive placebo who later receive izokibep, exposure will further be summarized by placebo and izokibep.

Adverse events and SAEs reported before first administration of study drug will be listed. All summaries will include only treatment-emergent events. The number of subjects who report one or more AEs, the number who report one or more severe AEs, the number who report one or more SAEs, and the number who report one or more AEs that leads to discontinuation of study drug will be summarized by treatment during the primary phase of the study and overall. Subjects who receive placebo during the primary phase will additionally be summarized by phase (placebo-controlled and after crossing over to active).

Laboratory data will be summarized at each planned collection timepoint. Subjects with positive ADA results will be summarized by timepoint.

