5.2.2. Handling of Missing Safety Data

In general, missing clinical laboratory data, vital signs, and ECG data will not be imputed. Adverse event imputations for missing severity or relationship are given in Section 6.7.2. Unknown or partial medication and AE date imputations are given below and are to be used only for the assessment of prior/concomitant status for medications and treatment-emergent status for AEs.

5.2.3. Handling of Partial and Missing Dates for Date of Birth, Adverse Events, Prior/ Concomitant Medications

Partial and Missing Dates of Birth

Where the Date of Birth is missing the following convention will be used:

Where the day is missing and month and year are available the day will be completed as the 15th. For example, Date of Birth specified as --JAN1980 will be completed as 15JAN1980.

Missing or Partial Adverse Event and Prior/Concomitant Medication Start/Stop Dates

Missing and/or incomplete dates for medications and AEs are imputed in a manner resulting in the earliest onset or the longest duration during the Treatment Period, whilst ensuring that the start date does not occur after the stop date. The stop date will not be imputed if the medication or AE is "Ongoing". Technically, this will be done as follows:

For a missing/incomplete start date/time the earliest date/time of the following will be imputed:

- The later date of: the earliest possible start date/time, and the date/time of the first dose of treatment.
- The latest possible start date/time.
- The latest possible stop date/time.

For a missing/incomplete stop date/time the later date/time of the following will be imputed:

- The earlier date/time of the latest possible stop date/time and the date/time of last dose of treatment.
- The earliest possible stop date/time.
- The earliest possible start date/time.

Here, the earliest possible date/time is defined as:

- The date/time itself if available.
- The date/time of the first day of the month at 00:00hrs, if month and year are available but the day/time is missing.
- The date/time of the first day of the year at 00:00hrs, if year is available but day/time and month are missing.
- 00:00hrs on the day of informed consent, if the date/time is completely missing.

The latest possible date/time is defined as:

- The date/time itself if available.
- The date/time of the last day of the month at 23:59hrs, if month and year are available but the day/time is missing.

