6.5. Measurements of Study Drug Compliance

Study Drug compliance is defined as the number of doses that were actually taken relative to the number of doses that should have been taken as per the protocol for the planned duration of treatment exposure. A partial dose in CRF will be treated as a half dose. Study drug compliance in Part B will be summarized for period 1 and period 2 separately.

In general, the percentage of overall compliance, assessed by dose count, will be calculated as follows:

For Part A

For Part B Period 1

For Part B Period 2

For Part A, the total number of doses expected to be administered from Week 0 to Week 31 is 32 for all subjects. For Part B, the total doses expected to be administered differs by treatment assignment: for QW dosing, the total doses expected to be administered is 16 for Period 1 and 16 for Part 2; for Q2W dosing, the total doses expected to be administered is 8 for Period 1 and 8 for Part 2.

The calculated percentage compliance will be categorized as:

- < 80% compliance
- $\geq 80\%$ compliance

Compliance will be summarized for the Safety Analysis Set for Part A (overall) and for Part B by treatment group and Period as follows:

- Number of doses will be presented by default summary statistics.
- Percent compliance will be presented by default summary statistics.
- Number and percentage of subjects within each of the compliance categories will be presented. Treatment compliance will be listed for the Safety Analysis Set. Missing data will not be imputed and only original data for those fields (for example, date fields) will be presented in the listing together with derived variables such as the calculated compliance (%) and exposure duration.

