6.7. Safety

For all Safety Tables, data in Part A and Part B will be summarized as follows, unless otherwise specified:

- Part A summarized with all subjects for the entire time (Week 0 to Week 32)
- Part B, for Period 1, will include the first 16 weeks until the first dose of treatment administered in Period 2 at or after Week 16, summarized by the randomized treatment arms and the combined placebo group (Placebo QW/ Placebo Q2W; Izokibep QW; Izokibep Q2W), and includes all subjects who received at least one dose of study treatment. AEs will be included if date of onset is on or after the day of the first dose received in Period 1 and before the date of the first dose received in Period 2. If a subject did not receive any dose of study treatment in Period 2, all AEs with onset on or after the day of first dose received in Period 1 through 4 weeks (28 days) after the last dose received will be included.
- Part B, Period 2, will include data collected on and after the first dose of study treatment administered at Week 16 visit (or after Week 16 visit, if Week 16 visit is missing), summarized by the randomized treatment groups (Placebo Izokibep QW; Placebo Izokibep Q2W; Izokibep QW; Izokibep Q2W), and includes all subjects who took at least one dose of study treatment in Period 2. AEs will be included if date of onset is on or after the day of first dose received in Period 2 through 4 weeks (28 days) after the last dose received.

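### SAP 6.7 counts Part B adverse events over 112 days before the Week 16 switch but 127 or 134 days after it, and most tables make no adjustment for time at risk

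*SAP*

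**What the plan says.** SAP 6.7 sets the two Part B safety windows. Period 1 "will include the first 16 weeks until the first dose of treatment administered in Period 2", and its events are those with onset from the first dose "and before the date of the first dose received in Period 2". A subject who never receives a Period 2 dose is instead followed in Period 1 to 28 days after the last dose (the rule that begins "If a subject did not receive any dose of study treatment in Period 2"). Period 2 events are those with onset "on or after the day of first dose received in Period 2 through 4 weeks (28 days) after the last dose received".

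The dosing calendar is in the footnotes to Protocol 1.3: "The last dose of study drug for subjects dosed QW is Week 31 and for subjects dosed Q2W is Week 30".

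SAP 6.7.2 reports numbers and percentages of subjects, with event counts added in the SOC/PT tables. Exposure is tabulated on its own in SAP 6.7.1 and is not used as a denominator for events. Kaplan-Meier analyses are planned for AESIs and injection site reactions (ISRs), and in SAP 6.7.3.1 for liver events.

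Protocol 9.3.5 adds a by-phase view: "Subjects who receive placebo during the primary phase will additionally be summarized by phase (placebo-controlled and after crossing over to active").

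**The concern.** The by-phase summary puts the placebo weeks and the izokibep weeks of the same subjects next to each other. A reader will naturally take a higher percentage in the second column as a sign of the drug. If the second column also has more days in which an event can be counted, part of any increase is simply extra time. Within Period 2, the QW groups are also observed for 7 days more than the Q2W groups, so that side-by-side reading is slightly uneven too.

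**Working it through.** **Plan's own figure first.** QW dosing at Weeks 0-15 gives 16 doses and at Weeks 16-31 another 16. Q2W dosing at Weeks 0, 2, ..., 14 gives 8, and at Weeks 16, 18, ..., 30 another 8. SAP 6.5 agrees: "for QW dosing, the total doses expected to be administered is 16 for Period 1 and 16 for Part 2", and 8 and 8 for Q2W. Dosing is balanced across the periods, so the imbalance comes only from the 28-day tail.

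**Window lengths.** Week w falls on Day 7w + 1. Week 16 is Day 113, Week 30 is Day 211 and Week 31 is Day 218.

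- Period 1, continuing subject: Days 1 to 112 = 112 days.
- Period 2, QW: 218 + 28 - 113 + 1 = 134 days; 134/112 = 1.196.
- Period 2, Q2W: 211 + 28 - 113 + 1 = 127 days; 127/112 = 1.134.

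**Expected percentage with no drug effect.** Assume a constant event rate and a 112-day risk r. The risk over d days is 1 - (1 - r)^(d/112). The values of r are assumptions, because the documents give no placebo adverse event rate.

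| Period 1 risk (assumed) | Period 2, Q2W (127 days) | Period 2, QW (134 days) | Rise, points |
|---|---|---|---|
| 10% | 11.3% | 11.8% | 1.3 to 1.8 |
| 20% | 22.4% | 23.4% | 2.4 to 3.4 |
| 40% | 44.0% | 45.7% | 4.0 to 5.7 |
| 60% | 64.6% | 66.6% | 4.6 to 6.6 |

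In a placebo group of 29, the largest rise is 29 x 0.066 = 1.9 subjects. The smallest, in a group of 28, is 28 x 0.013 = 0.4.

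**What would cancel it.** The Period 2 event rate would have to fall by 1 - 112/134 = 16% (QW) or 1 - 112/127 = 12% (Q2W).

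**Discontinuation.** This check used whole-week windows (16, 18 and 19 weeks), an assumed 50% risk, and last doses spread evenly over the earlier dosing weeks for those who stop. With 10% stopping in each period, the percentage still goes from 48.7% to 54.2% (QW) and from 48.4% to 52.2% (Q2W). With 10% stopping in Period 1, the rise disappears only if about 30% (Q2W) or nearly 40% (QW) stop in Period 2.

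**Which denominator to use.** The SAP 6.7.1 exposure duration ends on the last dose day. In Period 1 that is 15 x 7 + 1 = 106 days (QW) or 14 x 7 + 1 = 99 days (Q2W), against a 112-day event window. It is not the time at risk.

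**Window end stated three ways.** SAP 6.7 ends Period 2 at 28 days after the last dose. SAP 6.7.2 ends it 4 weeks after the Treatment Period, which itself runs to Week 32: 32 + 4 - 16 = 20 weeks from the switch. SAP 5.1.3 describes Week 32 as four weeks after the last dose, which fits neither Week 30 nor Week 31. Under the 6.7.2 reading the gap would widen, at least for SAEs, which are collected to the 8-week follow-up visit; other events are collected only to 4 weeks after the last dose.

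**The case against.** The summary is descriptive. Protocol 9.3.5 plans no safety p-values, and a before-and-after contrast is confounded with time on study and with dropout whatever the windows. The populations differ as well: Period 1 includes early stoppers, while Period 2 includes only subjects dosed again. All of this stands, and it limits the weight of the point.

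A reader might infer that the plan has no time-adjusted safety analysis. That is not so. SAP 6.7.2 plans Kaplan-Meier estimates for AESIs and ISRs over the full study and separately for Period 2, with Period 2 onset counted from the Week 16 dose and an estimate at Day 112. For those events this is already the matched window. ISRs are also summarized by injection visit, with only subjects injected at that visit in the denominator. The gap in this cover is that an AESI category with fewer than 3 events in an arm gets no such analysis.

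A reader might also want subject-year rates for ISRs. These would mislead: the number of injections is the same in both periods, so at equal risk per injection the rate would look about 12% (112/127) or 16% (112/134) lower after the switch.

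Finally, a reader might infer from SAP 5.2.3 ("Missing and/or incomplete dates for medications and AEs are imputed in a manner resulting in the earliest onset") that ambiguous events around the switch are always charged to placebo. The rule does lean that way. A month-only onset in the switch month goes to the first of that month, and a wholly missing date goes to the first dose. But an event imputed to the first of the month lands in Period 2 if the switch was on that day, and an event that worsens after the switch counts as a Period 2 TEAE under 6.7.2. The documents give no frequency of incomplete dates, so the effect cannot be sized.

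**Conclusion.** The point holds for the overall TEAE, SOC/PT, SAE and discontinuation percentages when the placebo phase is read against the phase after the switch. The windows are unequal on the face of SAP 6.7, and those tables do not correct for it. The expected artefact is about 1 to 7 points, or at most about 2 subjects per placebo group. That rests on a constant event rate and assumed 16-week risks of 10% to 60%; for rarer events it is smaller.

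Two stronger readings are not supported. One is that placebo subjects will show a rise: this is an expectation, which a falling event rate or heavy Period 2 discontinuation could hide. The other is that the placebo-controlled safety comparison is biased: the randomized arms share the same Period 1 rule, so that comparison is unaffected.

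This is a cheap improvement, not a flaw in the trial's main safety evidence.

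**What to change.** In SAP 6.7 and 6.7.2:

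- For the by-phase summary of placebo subjects, restrict Period 2 to its first 112 days and show later events separately. As an alternative or in addition, give TEAE, SAE and AE-discontinuation rates per 100 subject-years, with time at risk equal to the days in each period's own event window and not the 6.7.1 exposure duration.
- Leave ISRs on the planned per-injection and Kaplan-Meier summaries.
- Keep the partial-date rule identical for all arms in the randomized Period 1 tables. Changing it for placebo subjects only would take events out of the placebo column of that comparison. If wanted, add a sensitivity version of the phase summary alone that assigns ambiguous switch-month events to Period 2.
- Reconcile the end of the Period 2 window across SAP 6.7, 6.7.2 and 5.1.3.

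The cost is SAP wording, programming and extra table columns. No new data are needed. The downside is somewhat less precision from the truncated window.

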6.7.1. Extent of Exposure

Exposure will be reported for Period 1, Period 2, and for the entire study for the Safety Analysis Set. Exposure duration will also be summarized and will be calculated as (last dose [in the period of interest] – first dose [in the period of interest] + 1). The total number of doses taken and the total number of active doses of izokibep taken in each period (and overall for the study) as well as the total study will be reported.

Descriptive statistics will be presented for duration of exposure. The summary will include exposure duration, and number of doses administered, and number of doses of active izokibep administered (for the full study period summary only).

A listing of overall treatment exposure data, including the first and last dates of treatment will be presented together with compliance for the Safety Analysis Set. Further, study treatment administration data will be listed for the Safety Analysis Set.

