Part B is a randomized, double-blind, placebo-controlled, parallel group, dose-finding investigation to evaluate the efficacy, safety, and immunogenicity of izokibep in subjects with moderate to severe HS. Subjects will complete up to a 28-day screening period, followed by a 16-week double-blind treatment period. At completion of the Week 16 visit procedures, subjects randomized to placebo will be switched to active treatment in a blinded manner for the Week 16 dose through Week 30 (Q2W dose group) or Week 31 (QW dose group). Subjects randomized to izokibep will remain on the same dose through Week 30 (Q2W dose

group) or Week 31 (QW dose group). After their respective treatment periods, all subjects will enter a follow-up period that includes 2 visits to be completed at Week 39 and Week 45. For subjects that early terminate the follow-up visits should be completed 8-weeks (\pm 5 days) and 14 weeks (\pm 5 days) after the last dose of study drug.

Approximately 170 subjects will be randomized into 1 of 4 groups in a 1:1:2:2 ratio as follows:

- Group 1 (n = 28-29): placebo SC QW from Day 1 (Week 0) to Week 15, then izokibep SC 160 mg QW from Week 16 to Week 31.
- Group 2 (n = 28-29): placebo SC Q2W from Day 1 (Week 0) to Week 14, then izokibep SC 160 mg Q2W from Week 16 to Week 30.
- Group 3 (n = 56-57): izokibep SC 160 mg QW from Day 1 (Week 0) to Week 31.
- Group 4 (n = 56-57): izokibep SC 160 mg Q2W from Day 1 (Week 0) to Week 30.

Randomization will be stratified by any prior biologic/Janus Kinase (JAK) inhibitor used for HS (Yes/No) and Hurley Stage (II or III).

Subjects will complete study assessments according to the study visits outlined in the SoA in the protocol. Day 1 corresponds to the first dose of study drug. All subsequent visits will be scheduled based on the Day 1 visit.

Subjects in the QW dosing groups (Group 0 [Part A], Groups 1 and 3 [Part B]) will have study visits at screening, Day 1 (Week 0), and at Weeks 1, 2, 3, 4, 8, 12, 13, 14, 15, 16, 17, 20, 24, 28, and 32 as well as at the follow-up visits.

Subjects in the Q2W dosing regimens (Groups 2 and 4 in Part B) will have study visits at screening, Day 1 (Week 0), and at Weeks 2, 4, 8, 12, 14, 16, 18, 20, 24, 28, and 32 as well as at the follow-up visits.

Subjects assigned to placebo SC QW and placebo SC Q2W will be grouped into a single placebo group for comparison to each dosing regimen of izokibep for Part B. The primary endpoint will be assessed at Week 16.

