5.1.3. Treatment Period

Data collected on Day 1 will be assigned to the Treatment Period unless the time (HH:MM) of data collection and time (HH:MM) of the first dose of study drug are both recorded and the data collection time is before the time of the first dose of study drug. In this case, the assessment will be assigned to the screening period. If the time (HH:MM) of data collection is not recorded but the protocol and/or CRF includes an instruction to the effect that all Day 1 assessments are to be performed prior to the first dose of study drug, the data collected at Day 1 will be assigned to the screening period. However, adverse events and concomitant medications starting on Day 1, will be assigned to the Treatment Period, unless the time (HH:MM) demonstrates otherwise.

The Treatment Period is defined as the period from the date/time of the first dose of study drug to Week 32 (four weeks after the last dose) or early termination/end of treatment visit (within two weeks from the last dose).

Treatment will be divided into two periods, Period 1 and Period 2. In Part B, Period 1 will start at the first dose of study drug and end at Week 16 when Week 16 assessments are completed and before administration of study drug. Period 2 will start at the time of first administration of study drug at or after Week 16 and end at Week 32 or early termination/end of treatment visit.

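### SAP 6.7.1 measures exposure as the span from first to last dose, so compliant QW and Q2W subjects with the same 16-week period show 106 and 99 days, and the two periods do not sum to the whole study

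*SAP*

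**What the plan says.** SAP 6.7.1 computes exposure duration as "last dose [in the period of interest] – first dose [in the period of interest] + 1" and states that "Exposure will be reported for Period 1, Period 2, and for the entire study for the Safety Analysis Set". The same section also reports the number of doses taken and the number of active doses, and lists first and last treatment dates together with compliance.

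SAP 2.1 gives the Part B schedules. Weekly placebo: "placebo SC QW from Day 1 (Week 0) to Week 15, then izokibep SC 160 mg QW from Week 16 to Week 31". Two-weekly placebo: "placebo SC Q2W from Day 1 (Week 0) to Week 14, then izokibep SC 160 mg Q2W from Week 16 to Week 30". The izokibep groups receive "izokibep SC 160 mg QW from Day 1 (Week 0) to Week 31" or "izokibep SC 160 mg Q2W from Day 1 (Week 0) to Week 30".

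SAP 5.1.3 sets one period boundary for both schedules: "Period 1 will start at the first dose of study drug and end at Week 16", once the assessments at that visit are done and before dosing. Period 2 starts with the first administration at or after that visit.

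Protocol 9.3.5 describes exposure by doses administered and gives no formula in days. Nothing else in either document modifies the SAP formula.

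**The concern.** For a drug injected every 1 or 2 weeks, the treatment a subject has received does not end on the day of the last injection. The SAP formula stops the clock on that day. The time it leaves out depends on the dosing interval, so it falls unequally on the two regimens. A subject who stops after one injection is credited with 1 day. Yet SAP 6.7 counts that subject's adverse events through 28 days after the last dose if no Period 2 dose is given.

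At stake is how the exposure table of a two-regimen, dose-finding trial reads. It would show Q2W subjects as exposed for less time than QW subjects over an identical period, and combined placebo would average over the two scales. The Period 1 and Period 2 rows would also fall short of the whole-study row, by an amount that depends on regimen.

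**Working it through.** **Inputs.** Day 1 is the first dose (SAP 5.1.1), so the Week w dose is scheduled on Day 1 + 7w. Last scheduled doses are Week 15 (QW) or Week 14 (Q2W) in Period 1, and Week 31 or Week 30 in Period 2 (SAP 2.1). Period 2 starts with the Week 16 dose, Day 113. The assumption is full compliance, with every dose on its scheduled day.

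**Check against the plan's own figures.** The documents print no exposure duration in days, but SAP 6.5 states expected dose counts: "for QW dosing, the total doses expected to be administered is 16 for Period 1 and 16 for Part 2", and 8 and 8 for Q2W. Counting Weeks 0–15 and 16–31 in steps of 1 gives 16 and 16. Counting Weeks 0–14 and 16–30 in steps of 2 gives 8 and 8. The schedule is read correctly.

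**The SAP formula (last − first + 1).**

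| | QW | Q2W |
|---|---|---|
| Period 1 | 106 − 1 + 1 = 106 | 99 − 1 + 1 = 99 |
| Period 2 | 218 − 113 + 1 = 106 | 211 − 113 + 1 = 99 |
| Sum of periods | 212 | 198 |
| Whole study | 218 − 1 + 1 = 218 | 211 − 1 + 1 = 211 |
| Whole study minus sum | 6 | 13 |

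The difference between regimens is 106 − 99 = 7 days per period. A 1:1 pool of the placebo groups averages (106 + 99)/2 = 102.5 days in Period 1.

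**Dosing window.** Protocol 1.3 allows ±3 days. Moving only the last Period 1 dose within its window gives 103–109 days (QW) and 96–102 days (Q2W). The ranges do not overlap, so the window does not hide the difference among compliant subjects.

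**With the last interval credited (end date = last dose + interval − 1).**

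- QW: Period 1 ends on Day 106 + 6 = 112, giving 112 days. Period 2 ends on Day 218 + 6 = 224, giving 224 − 113 + 1 = 112. Whole study: 224.
- Q2W: Period 1 ends on Day 99 + 13 = 112, giving 112 days. Period 2 ends on Day 211 + 13 = 224, giving 112. Whole study: 224.

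The regimens agree, the periods sum to the total, and the values match the days that SAP 6.7.2 attaches to Week 16 (Day 112) and Week 32 (Day 224).

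**The case against.** The strongest reply is that the SAP states an explicit, reproducible measure and no passage requires exposure to equal the length of the period. SAP 5.1.3 defines periods, not exposure, and the Day 112 and Day 224 values in SAP 6.7.2 are Kaplan–Meier landmarks. A span naturally leaves out the gap between the last Period 1 dose and the first Period 2 dose. This stands: the formula is a definition poorly suited to its label, and calling it an arithmetic error would go too far.

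A reader might also infer that event rates will be inflated, by 112/106 = 1.057 for QW and 112/99 = 1.131 for Q2W, and so look about 7% higher for Q2W (106/99 = 1.07). The documents do not support that as a consequence of the plan. SAP 6.7.2 reports adverse events as numbers and percentages of subjects with event counts. Its time-to-event plots have their own censoring rules, and its weekly injection site reaction incidence uses subjects injected at that visit. The event windows in SAP 6.7 do not use exposure duration. The inflation would arise only if someone built person-time rates from the table, which is not planned.

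Dose counts, dose dates and compliance by period let a careful reader see what happened. Protocol 9.3.1 has the placebo schedules summarized separately as well as combined.

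Finally, crediting the dosing interval is itself a convention. It matches neither the 28-day event window nor the single-dose subcutaneous half-life of 278 hours (278/24 = 11.6 days, Protocol 2.2.3.4). This limits how much the alternative can claim. It does not explain why the default should build in a regimen-dependent shortfall.

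**Conclusion.** The point holds as a minor one. As defined, exposure duration for on-schedule, fully compliant subjects is 106 days (QW) or 99 days (Q2W) per 16-week period, and the period values fall 6 or 13 days short of the whole-study value. A single injection counts as 1 day on either schedule. The figures rest on the schedule in SAP 2.1 and on full compliance; actual values will vary with dose timing and missed doses.

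The effect is confined to the descriptive exposure summary. No hypothesis test, planned event rate or adverse event window changes, and the documents give no ground for concluding that the safety comparison between regimens is biased.

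**What to change.** In SAP 6.7.1, define the end of exposure in each period as the earliest of:

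- last dose date + assigned dosing interval − 1 day (interval 7 days for QW, 14 days for Q2W);
- the day before the first dose of the next period;
- the last date in the study.

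Duration is that end date minus the first dose date, plus 1. Full compliance then gives 112 + 112 = 224 days in every group.

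Two small downsides should be stated. A subject who stops after one injection is credited with 7 or 14 days depending on regimen. And the periods still do not sum to the total when the boundary is not fully covered: a QW subject who misses only the Week 15 dose gets 105 + 112 = 217 days, against 224 overall.

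If the current formula is kept, label it as time from first to last dose. Add a footnote that it differs by dosing interval and that the periods do not sum to the whole-study value.

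Either choice costs one definition or label in SAP 6.7.1 and the matching program. No data collection, design or dosing is affected.
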